The study included two interim analyses: on 15 and 30 percent of the recruited patients. Distribution of the first type error in accordance with the O'Brien–Fleming error waste function, of the second type – in accordance with the Pocock function. It is possible to stop the study early due to both acceptance and rejection of the null hypothesis. The interim analysis is based on the data obtained from the results of examination and treatment of the number of patients established by the protocol who completely completed participation in the study. Number of patients for the first interim analysis: 30 patients (MMN-MAP group - 15 patients, Placebo group - 15 patients). Number of patients for the second interim analysis: 60 patients (MMN-MAP group - 30 patients, Placebo group - 30 patients). Number of patients for the final analysis: 196 patients (MMN-MAP group - 98 patients, Placebo group - 98 patients).

Treatment

Group 1

Name of the medicinal product: MMH-MAP

Active ingredient: Modified affinity purified antibodies to S100 brain-specific protein - 0.006 g*.

* applied onto lactose monohydrate as a water-alcohol mixture containing no more than 10^{-391} ng/g active form of the API

Excipients: Lactose monohydrate - 0.267 g

Microcrystalline cellulose - 0.030 g

Magnesium stearate - 0.003 g

Method of administration: Tablet for oral use. 2 tablets twice daily (approximately at the same time), outside the meal (between meals or 15 minutes before meals or fluids). Keep the tablets in mouth until completely dissolved.

Dosage form: Tablets.

Description: Flat cylinder-shaped scored beveled edge white to off-white tablets with a smooth, uniform surface.

Storage conditions: At temperature ≤ 25 °C.

Group 2

Name of the medicinal product: Placebo

Active ingredient: No

Excipients: Lactose monohydrate - 0.267 g

Microcrystalline cellulose - 0.030 g Magnesium stearate - 0.003 g

Method of administration: Tablet for oral use. Dose per administration: 2 tablets. 2 tablets twice daily (4 tablets/day). The tablets should be held in mouth without chewing until complete dissolution.

Dosage form: Tablets.

Description: Flat cylinder-shaped scored beveled edge white to off-white tablets with a smooth, uniform surface.

Storage conditions: Store at a temperature not exceeding 25 ° C.

Treatment duration

MMH-MAP/Placebo treatment duration is 90 days.

Observation period

In total the patients will be monitored for 90 days.

Hospital stage - 12 days;

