Medical history	+			
Concomitant conditions and diseases	+			

Physical examination	+	+		+
Evaluation of vital				
signs (HR, RR, BP) ***	+	+		+
Recording therapy for				
concomitant diseases	+	+	+	+
Filling MoCA scale	+			+
Filling Glasgow scale	+			
Filling NIHSS scale	+	+		+
Filling mRs scale	+			+
Pregnancy test	+			
Safety laboratory tests	+			+
Inclusion/exclusion	+			
criteria				
Randomization	+			
Dispensing of study	+	+		
drug				
Study drug				
accountability and		+		+
return				
Treatment compliance		+		+
Evaluation of study	Ŧ	Ŧ	Т	–
treatment safety	т	Ŧ	Ŧ	т
Filling CGI-EI scale				+
Visit completion	+	+	+	+
Study completion				+

* The end of the inpatient period is the last day of hospitalization for the current stroke

** Study completion

**** HR - heart rate; RR - respiration rate; BP - blood pressure

Statistical Analyses

Samples

Total set includes all the subjects who have signed ICF. This sample will consider all adverse events (AEs) throughout the study, including those occurred prior to the study therapy.

The sample including all patients who received at least one dose of the study drug to be used for *analysis of the study treatment safety and tolerability* (*Safety population*), as all AEs identified after the study drug administration will be recorded.

Full Analysis Set This sample will consist of all enrolled patients, except for those who met at least one of the following criteria:

- 1) non-compliance with inclusion/exclusion criteria;
- 2) patient did not take any dose of study drug;
- 3) absence of any patient data after administration of study drug.

This was the best set for the Intention-to-treat method, so it will be used in the Intention-to-treat

efficacy analysis (ITT-analysis) of the study therapy.

Per Protocol set. This sample includes all patients who received full protocol therapy and completed all scheduled visits. This set will be used for *Per Protocol analysis (PP analysis) of efficacy of study therapy. Per Protocol set* will not include the patients whose data are fully or partially invalid for analysis due to a protocol deviation.

Protocol deviations resulting in full or partial data invalidity:

- 1. Violation of visit schedule.
- 2. Inappropriate distribution/issue of the study drug.
- 3. Prescription of prohibited therapy.
- 4. Increase or decrease of 25% or more in the amount of study therapy received.

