- 5. Inability to assess patient's objective compliance (adherence to therapy) according to the formula (e.g. loss of packaging).
- 6. Gross inconsistencies between source documents and CRF detected during monitoring or other authorized inspection.
- 7. Violations of the Informed consent procedure.
- 8. Non-compliance with the clinical study protocol procedures.
- 9. Inability to collect all patient's data used for evaluation of the study endpoints (e.g. lack of entries in source documents required for verification of inclusion/exclusion criteria, safety and efficacy criteria).
- 10. Other protocol deviations resulting in full or partial data invalidity.

Data treatment and all statistical calculations under the protocol will be made using SAS-9.4 statistical software.¹

Evaluation of sample size

The sample size was assessed in accordance with the following rules and assumptions:

- 1. Statistical assumptions:
 - 1.1 the power of statistical tests 'P = (1β) ' is 80% (the probability of correct rejection of the null hypothesis is 0.8)
 - 1.2 the probability of type 1 error 'a' is less that 5% (the probability of false acceptance of the alternative hypothesis is less than 0.05)
 - 1.3 statistical criteria of intergroup comparisons are two-sided, unless otherwise stated
 - 1.4 calculation of sample size will be based on the assumptions on the expected effect declared in the primary efficacy criterion of the protocol

¹ Holder of license: OOO "NPF "Materia Medica Holding", No. 70100045.

Protocol No. MMH-MAP-002 11-Jun-2019

- 1.5 ratio between sample sizes of MMH-MAP and Placebo sample sizes is 1:1 (1 MMH-MAP patient per 1 Placebo patient)
- 1.6 statistical hypotheses null and alternative hypotheses on the difference between study drug and placebo under the dosing regimen used:

H₀: $\mu_1 - \mu_2 = 0$ H_a: $\mu_1 - \mu_2 \neq 0$

where μ_1 - change in mean MoCA summary score in MMH-MAP group, μ_2 - change in mean MoCA summary score in Placebo group

1.7 calculation of sample size for statistical criteria was made using the following program code:

Proc seqdesign errspend Design nstages = 3 Info = cum (0.15,0.3,1) Method (alpha) = UNI (rho = 0.5 tau = 0) Method (beta) = UNI (rho = 0 tau = 0) Stop = both Alpha = 0.05 Beta = 0.2 Samplesize model = twosamplemean (meandiff = 1.3 stddev = 3.0) Run

1.8 terminal sample size will be determined using the formula:

$$N_T = N_{PP}/(1 - K_{\rm B})$$

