where N_T – terminal sample size; N_{PP} – result of calculation in c. 1.7 i.e. scheduled number of patients completing the study per protocol; K_B – withdrawal rate.

2. Assumptions on expected clinical study effects.

It is assumed that the difference between the changes in the mean total MoCA score in the Study Drug and Placebo groups on Day 90 of treatment will be at least 1.3 points with a standard deviation of at least 3.0 points.

Therefore, group size needed to compare Study Drug and Placebo will be **98** patients for each group. Given potential withdrawal of at least 20% patients ($K_B = 0.2$) during the study for various reasons, at least **246** patients will be required to sign informed consent, with **123** patients per group (see cl. 1.8).

Statistical criteria

All statistical calculations will be made using two groups of statistical criteria:

- parametric to obtain effective estimates for random parameters in case the relevant conditions of method/model applicability are not violated (e.g. sphericity, normality, risk proportionality, etc.)
- nonparametric in all other cases.

Parametric criteria

The application of parametric criteria will be accompanied by a check of models for applicability (e.g. Kolmogorov-Smirnov test, Shapiro-Wilk test).

The following parametric methods and approaches are supposed to be used:

- To evaluate the differences in continuous variables obtained in one group at two different visits – Student t-test for paired samples.
- 2. To evaluate time changes in parameters compared analysis of variance (ANOVA) or covariance (ANCOVA) modified with repeated measures.
- 3. In case of multiple comparisons of the groups various corrections for multiplicity will be used, e.g. Dunnett, Tukey, Scheffe, Holm adapted test, etc.
- 4. Generalized Linear Models and/or Mixed Linear Models will be used in case of abnormal data distribution.
- 5. Selection of the type of distribution, specification of factor and covariance structures of the model will be made using fit-statistics such as AIC (Akaike information criterion).

The following SAS software programs are supposed to be applied to the above listed tests and techniques:

- UNIVARIATE normality verification of the distributions under comparison
- CORR, MEANS calculation of descriptive statistics
- TTEST Student's test with all modifications
- GLM generalized linear models for studying temporal dynamics (ANOVA, ANCOVA)
- GENMOD generalized linear models

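### The sequential test is sized on and described for completers, an ITT analysis on the FAS is planned beside it, and nothing says which set decides

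*Combined protocol and SAP*

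**What the plan says.** All references are to the combined protocol and SAP.

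- **Number of subjects** plans 246 inclusions and expects at least 196 of them (98 per group) to complete every protocol procedure.
- **Interim analysis** sets looks at 30 and 60 patients, restricts the interim data to patients who finished the study in full, and then gives "Number of patients for the final analysis: 196 patients (MMN-MAP group - 98 patients, Placebo group - 98 patients".
- **Evaluation of sample size, items 1.7 and 1.8**: the output of the sequential design code is N_PP, the "scheduled number of patients completing the study per protocol". It is divided by (1 − 0.2) to reach 123 per group.
- **Samples**: the FAS is assigned to the intention-to-treat "efficacy analysis (ITT-analysis) of the study therapy", and the PP set to the "Per Protocol analysis (PP analysis) of efficacy of study therapy".

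No section ranks the two sets, says what happens if they disagree, or says how the sequential boundaries apply to a FAS larger than 196. The multiplicity item under Parametric criteria concerns comparisons among groups, not among analysis sets.

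**The concern.** The protocol has one primary hypothesis and two efficacy analyses of it. The sample size, the looks and the stated power all belong to completers, yet the analysis that respects randomisation is the one on the FAS.

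Completion here is not plausibly independent of outcome. An adverse event that ends study treatment, or a need for a prohibited medicine, is a withdrawal criterion, and prescription of prohibited therapy is also a PP exclusion. Antiepileptics are on the prohibited list, while epileptic episodes are a listed safety outcome. Patients who die also leave the completer set. A superiority test on what remains compares groups that randomisation no longer protects. PP membership is also partly a matter of judgement, because the last deviation in the list is a catch-all.

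If the two sets disagree, the plan as written supports either conclusion.

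**Working it through.** **Inputs.** Item 1.7 gives "Proc seqdesign errspend Design nstages = 3 Info = cum (0.15,0.3,1" and "Alpha = 0.05 Beta = 0.2 Samplesize model = twosamplemean (meandiff = 1.3 stddev = 3.0) Run", with an O'Brien–Fleming-type alpha shape, a Pocock-type beta shape and stopping for either reason. Item 1.3: "statistical criteria of intergroup comparisons are two-sided, unless otherwise stated". Item 1.1: "the probability of correct rejection of the null hypothesis is 0.8". Allocation is 1:1 and withdrawal is 20%.

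**1. The plan's own figure.** Solving this three-look two-sided design by numerical integration, with the acceptance boundary binding, gives a drift of 3.026 and rejection bounds |Z| of 4.84, 3.42 and 1.874.

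N = 4 × SD² × drift² / δ² = 4 × 9 × 3.026² / 1.3² = 195.05, or 97.5 per arm, rounded up to **98**.

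98 / 0.8 = 122.5, rounded up to **123** per arm and **246** in total. Both figures reproduce. Power at exactly 98 per arm is 80.2%. A fixed design would need 84 per arm, so the 98 belongs to this sequential design, and item 1.8 says it counts per-protocol completers.

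**2. Information fractions.** The looks at 30 and 60 are 30/196 = 15.3% and 60/196 = 30.6% of the completers, matching the code. Against 246 they are 12.2% and 24.4%. The schedule therefore does not carry over unchanged to a FAS near its ceiling.

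**3. Type I error if success on either set were accepted.** Take the PP set (98 per arm) as nested in the FAS, with no effect in either. The two final statistics then have correlation √(98/n_FAS); at 123 this is √0.797 = 0.893. The fixed-test column uses the bivariate normal at two-sided 5%. The sequential column simulates 4 million trials, with completer-based interims and both sets tested against 1.874 at the end.

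| FAS per arm | Fixed 5% tests | Sequential boundaries |
|---|---|---|
| 98 (sets coincide) | 5.0% | 5.0% |
| 105 | 6.2% | 6.0% |
| 110 | 6.5% | 6.3% |
| 123 | 7.1% | 6.7% |

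If one set is named in advance there is no inflation: 5.0% on completers, and about 4.8% on a FAS of 123 tested at 1.874 after completer-based interims.

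**4. Power on a FAS of 123 per arm.** The documents give no effect for non-completers, so two assumptions bracket it. If everyone gains 1.3 points, the drift is 1.3 / (3 × √(2/123)) = 3.398. If the 20% who do not complete gain nothing, the mean effect is 0.8 × 1.3 = 1.04 and the drift is 2.719.

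- Whole sequential test on the FAS: 87% and 72%.
- Interims on completers, final test on the FAS: 84% and 74%.

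All four figures require a Day-90 MoCA value for every FAS patient.

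**The case against.** The strongest reply is that the plan never says a win on either set is enough. A reader might infer two separate 5% chances, which for independent tests would give 1 − 0.95² = 9.75%. The documents do not support that. They are silent on the rule, and the sets overlap so heavily that even an either-set rule adds about 2 points at most under the planned numbers.

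A FAS of 123 per arm is also a ceiling. The 246 are described as signing consent; screening failures and eligibility errors are among the withdrawal reasons; and the FAS drops patients who were ineligible, undosed or without post-dose data. With 100 per arm in the FAS the fixed-test figure is only 5.7%. MoCA is scheduled only at Visits 1 and 4 and no imputation is described, so an observed-case FAS analysis could come close to the completer set. This limits the inflation, but it also shows that the ITT test itself is not defined.

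The Interim analysis section does not name the PP set. The link runs through Number of subjects and item 1.8, and the PP set, with its list of deviations, is narrower than completers as such. That is correct, and it leaves the deciding set still less clear.

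Finally, sizing on evaluable patients and inflating for withdrawal is openly declared and is not an error. A reader might infer that the ITT analysis is underpowered. The range in step 4 lies on both sides of 80%, so that does not follow either.

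**Conclusion.** The point holds as a gap with a definite consequence. The sequential design is sized on completers, its looks are described for completers, and no rule says whether that set or the FAS decides. The main risk is bias from deciding on a subset selected after randomisation; the documents give no basis for putting a size on it.

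The multiplicity risk is secondary and conditional. If either set could win, type I error is about 6.7% on the sequential boundaries (7.1% for fixed tests) with 98 PP patients within a FAS of 123 per arm, falling towards 5% as the sets converge. This assumes nested sets, no selection bias and a binding acceptance boundary. A PP set smaller than 98 would raise it somewhat: the fixed-test figure is 7.4% at 90 of 123.

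The 80% power is correct for 98 per group at 1.3 points and is not stated for the FAS. The 72–87% range rests on assumed effects and assumed complete Day-90 data in non-completers, so it is a sensitivity range and not a design figure.

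**What to change.** 1. In Interim analysis and Samples, state that the single confirmatory test of H₀, at each interim look and at the final analysis, is on the FAS by randomised arm, with information fractions computed on that set. State that the PP analysis is supportive and cannot by itself establish efficacy.
2. State how missing Day-90 MoCA is handled in that test, with a sensitivity analysis. Without this, item 1 cannot be carried out, because MoCA has no scheduled value between Visits 1 and 4.
3. In Evaluation of sample size, say that the 80% refers to 98 patients per group with Day-90 MoCA and a 1.3-point effect. If FAS power is shown, give it as a sensitivity range under stated assumptions about non-completers.

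**Cost:** wording, a missing-data analysis and possibly a less favourable stated power. None of these changes requires more patients. If the sponsor wanted 80% power under the full-dilution assumption (1.04 points), about 153 per arm in the FAS would be needed: 2 × 9 × 3.026² / 1.04² = 152.4.

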Design: double-blind, randomized, parallel group placebo-controlled clinical study of efficacy and safety of MMH-MAP in the treatment of cognitive disorders in patients with ischemic stroke in the carotid arteries.

The study will enroll hospitalized subjects of either gender aged 40-75 years old with verified diagnosis of ischemic stroke in the carotid arteries within 72 hours post debut having moderate cognitive disorders, moderate neurological deficit.

At Visit 1 (day 1) the subject's complaints and medical history will be collected, objective examination, safety laboratory tests (hematology, serum chemistry, urinalysis) will be performed. The investigator will evaluate the patient's level of consciousness using The Glasgow Coma Scale, intensity of cognitive disorders using The Montreal Cognitive Assessment (MoCA), condition using National Institute of Health Stroke Scale (NIHSS) and The Modified Rankin Scale (mRs). Concomitant therapy will be recorded and changes in cerebral CT/MRI will be evaluated. If the subject meets inclusion criteria and has no exclusion criteria, he/she will be randomized to MMH-MAP or Placebo group. The first dose of the study product should be taken within 72 hours post stroke debut.

At Visit 2 (day 12±3, end of hospitalization period - the last day of hospitalization due to the current stroke) complaints will be collected, objective examination findings will be recorded, monitoring of the prescribed and concomitant therapy will be performed, treatment safety, compliance and stroke severity according to NIHSS will be evaluated.

By the end of hospital therapy the subject will be switched to outpatient therapy with continuation of IMP and medical assistance designed for the treatment of stroke and its sequelae. At Visit 3 (day 45±7 days) the investigator will make a phone call to the subject evaluating the treatment safety.

At final Visit 4 (day 90±7 days) complaints will be collected, objective examination findings will be recorded, monitoring of the prescribed and concomitant therapy will be performed, treatment safety, compliance, condition according to NIHSS will be evaluated, mRs, Clinical Global Impression Efficacy Index (CGI-EI) will be filled. The investigator will perform MoCA testing. Safety laboratory tests (hematology, serum chemistry, urinalysis) will be carried out.

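### The two arms carry different written administration instructions, which could expose allocation if the text reaches labels or patient materials

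*Combined protocol and SAP*

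**What the plan says.** The Study design section describes the trial as follows: "Design: double-blind, randomized, parallel group placebo-controlled clinical study". The Treatment section then describes each product separately.

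- Group 1 (MMH-MAP), Method of administration: 2 tablets two times a day, with an instruction to keep to about the same time, and then "outside the meal (between meals or 15 minutes before meals or fluids). Keep the tablets in mouth until completely dissolved".
- Group 2 (Placebo), Method of administration: "Dose per administration: 2 tablets. 2 tablets twice daily (4 tablets/day"; then "The tablets should be held in mouth without chewing until complete dissolution".

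The physical description of the tablets is the same in both entries, as are the listed excipients and their amounts. The storage limit is also the same (25 °C), though phrased differently. No other section gives an administration instruction common to both arms, or says that the differences between the entries are only wording.

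**The concern.** In a placebo-controlled trial with matched tablets, everything the patient and site see should be the same in both arms, including how the tablets are to be taken. Here one arm has a written condition about meals and fluids that the other does not. Anyone who holds the protocol and hears or reads the instruction given to a patient could match it to an arm, and matched tablets would not prevent that.

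The outcomes make this worth attention. The Study design section has the investigator perform the MoCA, the primary endpoint, at Visit 4. NIHSS, mRS and CGI-EI are completed at the same visit, and no separate assessor is mentioned. Compliance is reviewed at Visits 2 and 4, which are also the visits at which post-baseline ratings are made, so talk about how tablets are taken could occur close to the rating. Apart from the blind, arms that follow different meal and fluid conditions differ in something other than the study drug.

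**Working it through.** The point is textual. The inputs are the Group 1 and Group 2 entries under Treatment, the Treatment duration and Observation period entries, the Study design section and the Schedule of study procedures.

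**Step 1. Set the two entries side by side.**

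| Element | MMH-MAP | Placebo | Weight |
|---|---|---|---|
| Tablets per dose, doses per day | 2, twice daily | 2, twice daily | Same |
| Tablet description | Same text | Same text | Same |
| Storage | Limit of 25 °C | Limit of 25 °C | Same limit, different phrasing |
| Meals and fluids | Condition stated | Not mentioned | Substantive and observable |
| Same-time instruction | Stated | Not mentioned | Weak |
| Handling in the mouth | Keep until dissolved | Hold until dissolved; chewing excluded | Possibly only drafting or translation |

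**Step 2. Check the one figure in the entries.** 2 tablets × 2 administrations = 4 tablets per day. This is the daily total that the placebo entry states. The MMH-MAP entry gives no total but implies the same one. The amount of product is therefore matched, and the difference lies in the instructions alone.

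**Step 3. Ask how the difference could reach a patient or rater.** Blinded staff do not know the arm and so cannot give arm-specific advice themselves. The difference can come through only if labels or leaflets differ by arm, or if someone who knows the arm does the counselling. The Schedule of study procedures lists IVRS registration and a personal code, but the document does not describe labels, leaflets or counselling. The route is neither shown nor excluded.

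**Step 4. Extent if the route exists.** 2 administrations per day × 90 days = 180 scheduled administrations per patient who completes treatment. By stage this is 2 × 12 = 24 in hospital and 2 × 78 = 156 as an outpatient, and 24 + 156 = 180. This counts how often the instruction would apply. It does not measure bias.

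**Step 5. Effect on the primary endpoint.** The documents contain nothing from which a shift in MoCA due to a broken blind could be derived, so none is given. The planned sample size does not depend on the administration text.

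**The case against.** The strongest reply is that the two entries differ without contradicting each other. The placebo entry is silent on meals, fluids and time of day; it neither permits nor requires anything different. The MMH-MAP entry is silent on chewing, but a tablet kept in the mouth until dissolved leaves little room for it. The storage lines say the same thing in different words, which suggests two product descriptions written or translated separately. The document also calls itself a protocol summary, so common labels and patient instructions may exist outside it.

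Most of this stands, and it limits the point in four ways that a reader might overlook.

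- A reader might infer that allocation is revealed. The documents do not show this, because no arm-specific label, leaflet or counselling is described.
- A reader might infer that, unless the blind is broken, one arm must be dosed against its own entry. That does not follow. Since one entry is silent where the other speaks, a single instruction could be consistent with both. This is a remark on logic, not on which instruction is right.
- A reader might suppose that ward staff would see the difference at mealtimes. No section mentions ward staff, supervised meals or observed dosing.
- A reader might want to express the bias in MoCA points. Any such figure would be a guess.

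The reply does not remove the difference over meals and fluids. That condition is substantive and observable, it is written for one arm only, and nothing in the document cancels it. If common patient materials already exist, the two entries still fail to state the common instruction and need the same correction.

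**Conclusion.** The text is wrong as written: a double-blind protocol should not give its arms different administration instructions. The meal and fluid condition carries the point. The same-time instruction adds a little, and the remaining differences may be only wording.

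The consequence is conditional. If the arm-specific texts reached labels, patient instructions or counselling, the patient or the rating investigator could infer the arm, and dosing conditions would differ between arms at up to 180 scheduled administrations per patient. This rests on two assumptions that the documents leave open: that the text is carried through as written, and that whoever sees the instruction can compare it with the protocol. It is a risk to the blind, not demonstrated unblinding, and its size on the MoCA scale cannot be stated.

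**What to change.** Reconcile the two method-of-administration paragraphs into one instruction, word for word identical for both arms, covering time of day, relation to meals and fluids, and handling in the mouth. Which instruction applies is for the sponsor to decide. Confirm that labels, patient instructions and any counselling text carry that same wording for every patient, and state this in the protocol.

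The cost is wording only, in the protocol and, where needed, in labels and patient materials. It needs no extra patients, visits or procedures.

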- MIXED mixed linear models.

Non-parametric criteria

Below are potential types of comparisons with relevant criteria:

- 1. To evaluate time changes in the parameters compared Friedman test, non-parametric analogue of analysis of variance with repeated measures.
- For frequency analysis of contingency tables 2×2 χ2 (if the frequency under comparison > 5) or exact Fisher's test (if one of the frequencies under comparison < 5).

- 3. Cochran-Mantel-Haenszel test (modified χ^2 test for multiple comparisons) to perform frequency analysis based on independent strata.
- 4. For frequency analysis of data on presence/absence of an event or outcome during repeated measurements (contingency tables with dependent strata) survival analysis.

To perform the above-mentioned nonparametric statistical analysis the following SAS procedures are to be used:

- FREQ Friedman test, χ2 test and/or exact Fisher's test; Cochran-Mantel-Haenszel test
- LIFETEST, PHREG survival analysis
- NPAR1WAY Mann-Whitney U-test

Safety parameters

Adverse events recorded during the study will be grouped into frequency tables by severity, seriousness and relationship with the study drug.

Data presentation

Descriptive statistics will be provided for each study continuous / interval variable. Numerical data will be presented by mean, standard deviation, min and max values. Comparisons suggesting statistical conclusion will have the relevant confidence intervals. Outliers will be analyzed individually. The data will be grouped by visits. The categorical variables will be presented as frequency tables by visits.

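### For MoCA and NIHSS, checks on the data choose between conflicting analysis routes, one of which does not test the difference in means that the hypothesis and stopping boundaries assume

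*Combined protocol and SAP*

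**What the plan says.** The rule opens the Statistical criteria section and has general scope: "All statistical calculations will be made using two groups of statistical criteria". The first group is "parametric to obtain effective estimates for random parameters in case the relevant conditions of method/model applicability are not violated", with normality among the examples of conditions. The second is "nonparametric in all other cases". The primary endpoint is not exempted.

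Under Parametric criteria: "The application of parametric criteria will be accompanied by a check of models for applicability (e.g. Kolmogorov-Smirnov test, Shapiro-Wilk test"). No significance level is given. Nor does the plan say whether raw values or residuals are checked, or when.

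Two further items in that list bear on the choice:
- Item 4: "Generalized Linear Models and/or Mixed Linear Models will be used in case of abnormal data distribution".
- Item 5: "Selection of the type of distribution, specification of factor and covariance structures of the model will be made using fit-statistics such as AIC".

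The methods listed for continuous scores are a paired within-group t-test, repeated-measures ANOVA or ANCOVA, and the Friedman test. The two-sample rank test appears only in the list of SAS procedures ("NPAR1WAY Mann-Whitney U-test"). No between-arm test is assigned to the primary endpoint.

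Under Evaluation of sample size, item 1.6 states the null hypothesis as a zero difference between arms in mean MoCA change. Item 1.7 derives the three-look design from "Samplesize model = twosamplemean (meandiff = 1.3 stddev = 3.0"). The Interim analysis section sets the looks at 15, 30 and 98 patients per arm.

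**The concern.** If the data fail the applicability check, the plan gives two answers. The general rule leads to a non-parametric test, and item 4 leads to a generalized or mixed linear model. AIC may then settle the distribution and the factors. The decisive primary analysis is therefore open until the data are examined, and two statisticians following the text could reach different tests.

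The routes are not interchangeable. The hypothesis, the assumed 1.3-point effect, the boundaries and the 98 per group all refer to a difference in means. A Mann-Whitney test asks whether values in one arm tend to exceed those in the other. That matches a difference in means under a pure location shift, but not when the arms differ in shape. MoCA is a bounded whole-number score, so a ceiling that bites harder in one arm is plausible. At stake is whether a significant result supports the stated claim, and whether all three looks apply their boundaries to the same statistic.

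**Working it through.** **1. The plan's own figure.** Inputs from item 1.7: difference 1.3, SD 3.0, two-sided alpha 0.05, beta 0.2, information fractions 0.15, 0.30 and 1, stopping for rejection or acceptance, unified family with rho 0.5 (alpha) and 0 (beta). Reject if |Z| ≥ C_a·t^(−0.5). Accept if |Z| < θ√t − C_b, where θ = C_a + C_b is the drift and the acceptance boundary is binding. Numerical integration gives C_a = 1.874, C_b = 1.152 and θ = 3.026.

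- N = θ²·4·SD²/δ² = 3.026² × 36 / 1.69 = 195.05, i.e. 98 per arm.
- With 20% withdrawal: 98/0.8 = 122.5, i.e. 123 per arm and 246 in all.
- Rejection bounds on |Z|: 4.84, 3.42, 1.874. Acceptance bounds: 0.02, 0.51, 1.874.

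The stated size is reproduced by a comparison of two means, so that is the statistic the boundaries belong to.

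**2. How often a check would switch the test.** Assumptions not in the documents: Shapiro-Wilk at 5% in each arm on the raw values, failure in either arm triggers the switch, and Mann-Whitney is the alternative. There were 6,000 simulated trials per scenario. The last column applies only if the check is repeated at each look.

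| Data, same distribution in both arms | Switch at 15 / 30 / 98 per arm | Test not the same at all three looks |
|---|---|---|
| Exactly normal, SD 3 | 9% / 10% / 9% | 22% |
| Normal, SD 3, rounded to whole points | 15% / 19% / 45% | 53% |
| Normal(25, SD 4), rounded, capped at 30 | 27% / 59% / 100% | 78% |
| Left-skewed, SD 3 | 63% / 94% / 100% | 38% |

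Two independent 5% tests alone give 1 − 0.95² = 9.75%, which is the first row. The rise to 45% in the second row comes from rounding.

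**3. The same check on residuals.** Testing pooled residuals from a baseline-adjusted model (assumed baseline slope 0.6, rounded scores), Shapiro-Wilk rejects in about 4% to 6% of trials at each look. The route then differs between the second look and the final analysis in about 8%, against about 41% to 42% for the raw-change check.

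**4. Effect on error rates, using the bounds from step 1.**

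| Scenario | Switching procedure rejects | t-test throughout rejects |
|---|---|---|
| Same shape in both arms, no effect (four cases above) | 0.049 to 0.056 | 0.048 to 0.056 |
| Equal means and SD 3, left-skewed vs normal | 0.106 | 0.048 |
| Equal means and SD 3, left- vs right-skewed (extreme) | 0.349 | 0.057 |
| Difference 1.3, normal | 0.80 | 0.81 |
| Difference 1.3, rounded normal | 0.79 | 0.80 |
| Difference 1.3, left-skewed | 0.90 | 0.80 |

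Monte Carlo standard error: √(0.05 × 0.95/6000) ≈ 0.003 near 0.05, and √(0.8 × 0.2/6000) ≈ 0.005 near 0.80.

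In rows 2 and 3 the null of item 1.6 is true, so the excess over 0.05 is false rejection of the stated hypothesis.

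**The case against.** The strongest defence is that the text is softer than a mechanical gate. The check accompanies parametric methods, the normality tests are only examples, and no threshold is set. Item 4 would keep non-normal data in a model-based, generally mean-based analysis. If the check is made on model residuals, a switch may be rare (step 3). When both arms share one shape, error rates barely move. All of this stands, and it limits the size of the problem. It does not remove it: the general rule still says non-parametric otherwise, item 4 contradicts it, and nothing says which prevails for the primary.

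A reader might also infer several stronger things that the documents do not support:
- **That every outcome is affected.** The proportion with mRS 0-1 goes to chi-square or Fisher by cell frequency. The issue concerns the MoCA and NIHSS scores.
- **That the test will change between looks.** The plan does not say that the check is repeated. It only fails to rule this out.
- **That alpha is inflated in general.** With equal shapes it is not.
- **That the method is chosen on unblinded interim data.** The plan does not say who sees those data or when the method is chosen.
- **That the rule displaces a named primary test.** None is named.
- **That a rank analysis can give no interval for the effect.** Under a location shift, a Hodges-Lehmann interval estimates the same shift.

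**Conclusion.** The concern holds for MoCA and NIHSS. The plan has conflicting, data-dependent routes to the analysis, no fixed between-arm test for the primary, and nothing that keeps the test the same across the three looks. One route tests a hypothesis that in general is not the one stated.

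The frequency of switching is scenario-dependent. The 15%, 19% and 45%, and the 53% of trials without one constant test, rest on the raw-value, per-arm 5% check and on rounded normal change. A residual check could give far lower rates, and a marked ceiling or skew higher ones. The harm to inference arises when means are equal but shapes differ: about 10% rejection against about 5% for left-skewed versus normal arms. The 0.349 figure is an extreme case and should not be read as typical. This should be corrected before the first interim analysis. It does not undermine the sample size.

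**What to change.** For MoCA and NIHSS, delete the normality-based choice and the AIC selection of distribution and factors, and remove the conflict with item 4.

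For MoCA, specify one between-arm ANCOVA of the day-90 score on arm and baseline MoCA, with the same terms at all three looks and the stated boundaries. This must be newly written. The ANCOVA now listed is a repeated-measures form for time changes, whereas the Schedule of study procedures has MoCA only at Visits 1 and 4. With baseline in the model, the arm effect is the same whether the outcome is the day-90 score or the change, so it serves both the endpoint wording and item 1.6. Use an analogous fixed mean-based model for NIHSS. Keep Mann-Whitney (NPAR1WAY) as a sensitivity analysis. Lock the text before the first interim.

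The cost is wording only, and 98 per arm (246 enrolled) stands. In the simulations, the t-test used throughout, as a simple stand-in for the fixed mean-based model, held type I error at 0.048 to 0.057 and power at 0.80 to 0.81. The downside is losing the freedom to switch tests, and possibly some power if the data are strongly skewed (0.80 against 0.90 in the left-skewed scenario).
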